## Statistical Analysis Plan Template

Sponsor:	ProQR Therapeutics		
Protocol:	PQ-110-002		
Document Version No.:	1.0	Document Date:	04 JAN 2022

AE is treatment-emergent if the AE start time was not recorded or was after the time of the first dosing of study treatment on Day 1.

An ocular TEAE following the first dose of study treatment is an ocular adverse event that was not present prior to administration of the first dose of study treatment but was present after the first dose, or an event with onset prior to the first dose with an exacerbation of the event after the first dose.

A non-ocular TEAE is a non-ocular adverse event with onset after the first dose of study treatment, or an event that was present prior to the first dose which had an exacerbation (worsening) occurring after the first dose.

If an ocular TEAE affects both eyes, it will be listed and summarized as two ocular TEAEs, affecting the first treated and contralateral eye. If a subject has multiple TEAEs which are coded to the same PT within the same SOC, that PT will only be reported once for that subject. Similarly, if a subject has multiple TEAEs which are coded to different PTs within the same SOC, that SOC will only be reported once for that subject.

In summaries of TEAEs by relationship, if there is more than one occurrence of a particular event for a subject, the event of most related will be included in the summary tables of TEAEs. In addition to presenting TEAEs by each relationship category (possibly related, probably related, and definitely related ), as indicated for the event by the Investigator, TEAEs will be summarized by the categories as being either related or not related, where an TEAE will be considered related to study treatment if the event is at least 'possibly' related (i.e., to include 'possibly related', 'probably related' and 'definitely related') or if the relationship is missing.

In summaries of TEAEs by severity, if there is more than one occurrence of a particular event for a subject, the event of greatest severity will be included in the summary tables of TEAEs. In summaries of TEAEs by both severity and relationship, the most severe of the TEAEs will be included in the summary tables of TEAEs.

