### 9.3.1 Assessment of Severity (Intensity) of Adverse Events

On the AE eCRF, the Investigator will use the adjectives MILD, MODERATE, or SEVERE to describe the maximum intensity of the AE. For purposes of consistency, these intensity grades are defined as follows:

- MILD: Does not interfere with subject's usual function.
- MODERATE: Interferes to some extent with subject's usual function.
- SEVERE: Interferes significantly with subject's usual function.

As described previously in [Section 9.2.2](#), note the distinction between the severity and the seriousness of AE. A severe event is not necessarily a serious event. For example, a headache may be severe (interferes significantly with subject's usual function) but would not be classified as serious unless it met one of the criteria for SAEs, listed above in [Section 9.2.2](#).

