### **10.6 Safety Analyses**

#### **10.6.1 Treatment Emergent Adverse Events**

A treatment emergent adverse event (TEAE) is defined as an event that was not present prior to administration of the first dose of study drug and present after the first dose or if it represents the exacerbation of an event that was present prior to the first dose.

Adverse events noted during the study will be coded to system organ classes (SOCs) and preferred terms (PTs) using the Medical Dictionary for Regulatory Activities (MedDRA) dictionary. The overall incidence of TEAEs will be summarized by dose group and classified by SOC and PT. Deaths, AE severity, seriousness, relationship to study drug and study discontinuation due to AE will also be tabulated by dose group. An AE will be considered drug-related if the Investigator indicated the event is at least “possibly” related or if the relationship is missing. Adverse events with missing start dates, but with stop dates overlapping into the treatment period will be counted as treatment emergent. All AEs will be listed in subject listing and summarized by numbers and percentages of subjects by dose for each portion of the study separately. If a subject reports the occurrence of a particular event more than once, the most severe of those events will be included in the summary tables of TEAEs, and the most severe of the treatment-related events will be included in the summary tables of TEAEs.

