#### 4.7.1. Adverse Events

Adverse events will be coded using the Medical Dictionary for Regulatory Activities (MedDRA) Version 20.0 and displayed in tables and listings using System/Organ/Class (SOC) and Preferred Term.

Adverse events are summarized by subject frequencies, therefore, in any tabulation, a subject contributes only once to the count for a given adverse event (SOC or preferred term).

A treatment emergent adverse event (TEAE) is defined as an event that was not present prior to administration of the first dose of study drug and present after the first dose or if it represents the exacerbation of an event that was present prior to the first dose.

The number and percentage of subjects with any TEAE, with any TEAEs assessed by the Investigator as related to study drug and those related to drug administration (definite, probable, or possible relationship), and with any serious adverse event will be summarized by treatment group and overall. Deaths, TEAE severity, seriousness, outcomes (resolved, resolved with sequelae, not resolved, resolving, fatal and unknown) and study discontinuation due to TEAE will also be tabulated by treatment group. In these tabulations, each subject will contribute only once (i.e., the most related occurrence or the most severe occurrence) to each of the counts in the descriptive analysis, regardless of the number of episodes. No formal hypothesis-testing analysis of adverse events will be performed.

Missing or partial start and end dates will be imputed as described in Section 4.2.9.3 before determining whether an AE is treatment emergent. For subjects with an actual or imputed AE start date on Day 1, the

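### The SAP's severity-by-relationship AE tables can show a subject only as not related when a milder related occurrence exists, an undeclared departure from protocol 10.6.1

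*SAP*

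**What the plan says.** Protocol 10.6.1 makes two selections when an event recurs in a subject. The first is by severity alone: "If a subject reports the occurrence of a particular event more than once, the most severe of those events will be included in the summary". The second concerns related events: "the most severe of the treatment-related events will be included in the summary tables of TEAEs". The same section defines relatedness broadly: "An AE will be considered drug-related if the Investigator indicated the event is at least “possibly” related or if the relationship is missing". Severity has three levels (protocol 9.3.1): "the Investigator will use the adjectives MILD, MODERATE, or SEVERE to describe the maximum intensity of the AE".

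SAP 4.7.1 sets a separate rule for each type of table:

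- Severity-only tables keep the occurrence of greatest severity.
- Relationship-only tables keep the most related occurrence.
- Tables by both follow one selection: "In summaries of TEAEs by both severity and relationship, the most severe of the TEAEs will be included".

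The same SAP section says that a subject is counted once per SOC or preferred term in any tabulation. It splits ocular events into four eye categories: first treated eye, treated contralateral eye before its first dose, the same eye after that dose, and non-treated contralateral eye. It lists four severity-by-relationship tables: ocular and non-ocular, each by relationship to study treatment and by relationship to administration.

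SAP 1.2 undertakes to outline differences from the protocol. Section 5, which lists the changes, does not mention this one.

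**The concern.** The SAP carries over the first of the protocol's two selections and drops the second in the tables where the second would have an effect. Suppose a subject has one moderate related and one severe unrelated occurrence of the same term. The cross-table places that subject under severe and not related, and nowhere else. The relationship-only table records a related event without its severity. The severity-only table records severe without attribution. The severity of the related event then appears in no planned summary table.

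The situation can plausibly arise in this study. Dosing repeats every 6 months per eye (protocol 2.3.1), and SAP 4.5 allows for up to 7 doses per eye. Recurrent events are recorded individually, and a persistent event that worsens is recorded again (protocol 9.4.3.2). Causality is judged separately for the drug and for the injection (protocol 9.3.2), so occurrences of one term in one eye can carry different attributions. What is at stake is whether a reader of the summary tables can see how severe the drug-related events were.

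**Working it through.** The documents give no figure on this point, so there is nothing to reproduce. The check compares the two rules and then applies each to every possible case of two occurrences.

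**Inputs.** Three severity levels (protocol 9.3.1); two relationship classes, related (including missing) and not related (protocol 10.6.1, SAP 4.7.1); one count per subject per term (SAP 4.7.1); at most 11 subjects (protocol 5.1).

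**Enumeration for one subject and one term.** Each occurrence can take 3 × 2 = 6 forms, so two occurrences give 6 × 6 = 36 ordered pairs. Pairs with no related occurrence: 3 × 3 = 9. Pairs with at least one: 36 − 9 = 27, made up as follows.

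- Both related: 3 × 3 = 9. The SAP rule keeps a related entry.
- One related, one not: 2 × 3 × 3 = 18. In 6 the related occurrence is the more severe and is kept. In 6 the severities tie, and the SAP gives no tie-break. In 6 the unrelated occurrence is the more severe, and the related one drops out.

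The 6 masked pairs are three combinations, each in two orders:

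| Related occurrence | Unrelated occurrence | SAP cross-table | Protocol 10.6.1 selections |
|---|---|---|---|
| mild | moderate | moderate, not related | moderate, not related; mild, related |
| mild | severe | severe, not related | severe, not related; mild, related |
| moderate | severe | severe, not related | severe, not related; moderate, related |

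The SAP rule therefore loses the related entry in 6 of 27 pairs, before ties are considered. The protocol's two selections lose it in 0 of 27. These counts show the mechanism; they are not expected frequencies.

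**SOC level.** Because the count is also once per SOC, a milder related event can be hidden there by a more severe unrelated event with a different preferred term.

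**Scale.** One masked subject changes the related percentage for a term by 100/n points, where n is the column denominator. With n = 11 this is 100/11 = 9.1, and any smaller n gives more. SAP 4.2.2 groups first treated eyes by their PQ-110-001 regimen, of which it names two, but gives no group sizes. If all 11 subjects were split between two groups, the smaller would hold at most 5, and one subject would be at least 100/5 = 20 points there.

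**The case against.** The strongest reply is that little is lost, and much of it stands.

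- **Primary endpoint.** A reader might infer that the primary endpoint is compromised. It is not. The endpoint is the frequency and severity of ocular and non-ocular AEs regardless of cause, and the severity-only tables keep the greatest severity.
- **Disappearance.** A reader might infer that the related event vanishes from the report. It does not. It counts in the relationship-only tables, and its severity can be read in the AE listings. With no more than 11 subjects and no hypothesis tests on AEs, case-by-case reading is feasible.
- **Reach of the protocol rule.** Protocol 10.6.1 speaks of treatment-related events and gives no selection rule for administration-related ones. The direct conflict therefore covers two of the four tables. The protocol also does not name the table for its second selection, and protocol 10.1 leaves table formats to the SAP. That softens the conflict but does not remove it: a severity-by-relationship table is where the second selection has effect, and the SAP's declared changes do not include dropping it.
- **Direction.** The SAP rule also hides a mild unrelated occurrence behind a severe related one, and counting a missing relationship as related errs against the drug. Both are true. Compared with the protocol's rule, though, the SAP rule can only remove related entries from these tables and never adds one.

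**Conclusion.** The point holds in a limited form. On the SAP's wording, a severity-by-relationship table can classify a subject solely as not related for a term, within an eye category for ocular events, although a milder related occurrence exists. This departs from protocol 10.6.1 for the two study-treatment tables and is undeclared. For the two administration tables it is a matter of consistency. What is missing is the severity of the masked related event in any summary table.

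The scale is at least 9.1 points per masked subject per term, and more within a treatment group. It is tempting to read this as a 9.1-point bias in favour of the drug. The documents do not support that: it is the effect of one such subject, and nothing in them shows how many there will be. Masking at preferred-term level requires the same subject, the same term, the same eye category where ocular, different attributions, and the unrelated occurrence being the more severe. The conclusion assumes that the SAP sentence is programmed literally together with its count-once rule.

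**What to change.** Amend SAP 4.7.1 as follows:

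1. In the two study-treatment cross-tables, include each subject's most severe occurrence of a term and also the most severe treatment-related occurrence, as in protocol 10.6.1.
2. In the two administration cross-tables, apply the same rule to administration-related occurrences, for consistency.
3. Where occurrences tie on severity, use the more related one.
4. Except these four tables from the sentences in 4.7.1 that let a subject count only once per preferred term or SOC. Otherwise the new rule would contradict them.

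If the sponsor prefers to keep the present rule, it should be declared and justified in SAP section 5.

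The cost is a change of wording and one programming change, with no new data. The downside is that a subject may appear in both relationship columns for one term, so the columns may add to more than the number of subjects with the event. A footnote can explain this.

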## Statistical Analysis Plan Template

Sponsor:	ProQR Therapeutics		
Protocol:	PQ-110-002		
Document Version No.:	1.0	Document Date:	04 JAN 2022

Unless otherwise stated, the following summaries of TEAEs will be presented for all non-ocular TEAEs, and separately for ocular TEAEs in the first treated eye , in the treated contralateral eye before the first dose in the study , in the treated contralaertal eye after the first dose in the study and in the non-treated contralateral eye. Unless otherwise stated, any summary of any type of TEAEs or serious adverse events (SAEs) which includes the SOC and PT of the events, will order the SOC and the PTs within the SOC in alphabetical order.

The tables that provide an overview of TEAEs will be presented by treatment group, to include the number (and percentage) of subjects who had any TEAE, SAE, TEAE leading to discontinuation from study treatment, TEAE leading to discontinuation from the trial, deaths and will summarize the number of subjects who had a TEAE by severity, by relationship to study treatment and by relationship to study treatment administration.

The adverse events that were identified by the Investigator as meeting the definition of an adverse event of special interest (AESI), as defined in Section 9.2.4 of the clinical study protocol will be supplemented by events for which an AESI has been defined but for which are not meeting the criterion for an AESI.

The following summary tables will be produced:

- Overview of Non-ocular TEAEs
- Overview of Ocular TEAEs
- Non-ocular TEAEs by, SOC and PT
- Treatment-emergent AESIs
- Non-ocular TEAEs by Severity
- Ocular TEAEs by Severity
- Non-ocular TEAEs by Relationship to Study Treatment
- Ocular TEAEs by Relationship to Study Treatment
- Non-Ocular TEAEs by Severity and Relationship to Study Treatment
- Ocular TEAEs by Severity and Relationship to Study Treatment

## Statistical Analysis Plan Template

Sponsor:	ProQR Therapeutics		
Protocol:	PQ-110-002		
Document Version No.:	1.0	Document Date:	04 JAN 2022

- Non-ocular TEAEs by Relationship to Study Treatment Administration
- Ocular TEAEs by Relationship to study Treatment Administration
- Non-ocular TEAEs by Severity and Relationship to Study Treatment Administration
- Ocular TEAEs by Severity and Relationship to study Treatment Administration
- Non-ocular Treatment-emergent SAEs
- Ocular Treatment-emergent SAEs
- Non-OcularTEAEs Leading to Discontinuation from Study Treatment
- Ocular TEAEs Leading to Discontinuation from Study Treatment
- Non-Ocular TEAEs Leading to Discontinuation from the Study
- Ocular TEAEs Leading to Discontinuation from the Study

Listings for AEs, and SAEs will be generated separately for ocular and non-ocular events. A listing of AESIs will be provided, as well as a listing of AESIs as defined in the protocol for events that do not meet the criteria for an AESI . Additionally, listings of AEs leading to death will be generated.

### 4.7.2. **Laboratory Data**

Observed values and change from baseline in each hematology and clinical chemistry parameter will be summarized by treatment group, age category and scheduled study visit by using descriptive statistics (number of subjects, mean, standard deviation, median, minimum, and maximum) for the continuous data and frequencies and percentages for the categorical data.

Hematology, clinical chemistry and urinalysis data, and changes from baseline, will be presented in subject listings.

### 4.7.3. **Vital Signs and Physical Examinations**

Vital signs measurements will consist of height, weight, heart rate, blood pressure and oral temperature. Descriptive summaries (number of subjects, mean, standard deviation, median, minimum, and maximum) of actual values and changes from baseline will be presented for each time point. These summaries will

## Statistical Analysis Plan Template

Sponsor:	ProQR Therapeutics		
Protocol:	PQ-110-002		
Document Version No.:	1.0	Document Date:	04 JAN 2022

be presented for the Safety Population and by treatment group.

By-subject listings of vital signs data and complete and symptom-directed physical examinations (urogenital exams not required) findings will be presented in a data listing.

### 4.7.4. **Electrocardiogram**

12-lead electrocardiogram (ECG) data will be presented in a listing.

### 4.7.5. **Ophthalmic Examination**

A single summary and listing will be generated to summarize the slit-lamp bio-microscopy examination, lens opacity grading, intraocular pressure (IOP) monitoring and dilated fundus examinations. Data will be summarized by treatment group (see Section 4.2.2), eye (first treated eye contralateral eye and non-contralateral eye) and visit using continuous and categorical summary statistics.

#### 4.7.5.1. **Slit-Lamp Bio-microscopy Examinations**

Slit-lamp bio-microscopy examinations of the eyelid/lashes, conjunctiva palpebral, conjunctiva bulbar, cornea, iris, anterior chamber, anterior chamber cells, anterior chamber flare, and lens examination will be summarized by treatment group, eye (first treated eye and contralateral eye) and visit. With the exception of presence of hypopyon (recorded as Yes, No), anterior chamber cells, and anterior chamber flare, the results will be graded as normal, abnormal not clinically significant or abnormal clinically significant.

Results for assessments of anterior chamber cells will be recorded as 0 (no cells / <1), 0.5+ or trace (1 5 cells), 1+ (6 15 cells), 2+ (16 25 cells), 3+ (26 50 cells), or 4+ (>50 cells), and anterior chamber flare recorded using the Standardization of Uveitis Nomenclature (SUN) Working Group Grading Scheme: 0 (none), 1+ (faint), 2+ (moderate / iris and lens details clear), 3+ (marked / iris and lens details hazy), or 4+ (intense/ fibrin or plastic aqueous).

## Statistical Analysis Plan Template

Sponsor:	ProQR Therapeutics		
Protocol:	PQ-110-002		
Document Version No.:	1.0	Document Date:	04 JAN 2022

### 4.7.5.2. Cataract (Lens Opacity) – Grading

Nuclear opacity, cortical opacity and posterior subcapsular opacity will be graded using the Age-Related Eye Disease Study (AREDS) lens grading system on a 7-unit scale (<1, 1, 1.5, 2, 2.5, 3, >3).

### 4.7.5.3. Dilated Fundus Examinations

A dilated fundus examination of the vitreous, vitreous cells, vitreous flare/haze, macula, optic nerve, peripheral retina, choroid and cup-to-disc ratio will be performed at each visit. Except for vitreous flare/haze, vitreous cells and cup-to-disc ratio, the results will be graded as normal, abnormal not clinically significant or abnormal clinically significant. Grading of vitreous flare/haze and vitreous cells will follow the National Eye Institute Grading System. For vitreous flare/haze, the results will be recorded as 0 (clear, no inflammation present), 0.5+ (trace inflammation present), 1+ (few opacities, mild blurring, clear optic disc and vessels), 2+ (significant blurring, hazy optic disc and vessels), 3+ (optic disc visible, no vessels seen), 4+ (dense opacity obscures optic disc, optic disc not visible). For vitreous cells, the results will be recorded as 0 (0-cells), 0.5+ (1-10cells), 1+ (11-20cells), 2+ (20-30cells), 3+ (30-100cells), or 4+ (>100 cells). Cup-to-disc ratio will be assessed in the dilated fundus examination on a 0.1 to 1.0 scale in increments of 0.1.

### 4.7.5.4. Intraocular Pressure

Intraocular pressure (IOP) will be measured in each eye by the examiner (different equipments might be used between visits) and the results will be recorded in mmHg at screening, dosing and follow -up visits.

### 4.7.6. Optical Coherence Tomograph (OCT)

Optical coherence tomography (OCT) will measure full retinal thickness (FRT), outer nuclear layer (ONL) thickness, presence of macular edema, and photoreceptor outer segment layer thickness (PROST) performed by an independent reading center according to the schedule of events (Section 2.4). The OCT values will be summarized by treatment group, eye and visit for the Safety Population using continuous descriptive statistics or categorical descriptive statistics. OCT data and any comments that may be relevant to the OCT grading will be listed for each subject in the Safety Population. The measures listed

## Statistical Analysis Plan Template

Sponsor:	ProQR Therapeutics		
Protocol:	PQ-110-002		
Document Version No.:	1.0	Document Date:	04 JAN 2022

below, regardless of confidence score (high confidence, adequate confidence, inadequate confidence) will be used for summaries and listings.

The following categorical data are collected as part of the OCT assessments:

- Confidence Score
- Confidence Score Reason
- Presence of Cystoid Macular Edema
- Additional Retina Morphology on Any Scan:
- Vitreous Debris/Cells
- Epiretinal Membrane
- Normal Retina/Fovea Contour
- Retinal Striae
- Foveal Distortion
- Adverse event of special interest (AESI) parameters

- Final AESI determination
- AESI comments OCT related comments

The following continuous data are collected as part of the OCT assessments, and are measured in mm:

